#### **6.3.4 Double-blind Treatment Period**

The double-blind treatment period for each study drug arm will vary based on when the subject was enrolled and may last from 4 up to 7 years (364 weeks [V93]) or until early termination, whichever is sooner. Subjects will continue treatment with the assigned study drug until every subject randomized to that study drug arm has received a minimum of 4 years (208 weeks) of treatment or is withdrawn. After the double-blind treatment period is completed, subjects may be eligible to continue treatment in an open-label extension if the study drug arm demonstrates a potential for clinical benefit.

*Location:* Monthly procedures/contacts may be accomplished at/by the DIAN-TU site, at the subject's home, or other trial-identified location with the trial-designated home health nurse. Annual visits will take place at the host DIAN-TU site.

*Time/Timing:* Every 4 weeks (+/- allowed visit window) until the last subject in a study drug arm has completed their year 4 visit, or the study drug arm has been terminated. Refer to the drug-specific appendices for allowable visit windows.

Visit duration depends on specific visit and study drug (e.g., infusion time, observation time after infusion). Note that annual visits may take place over 3-4 days. For subjects who live near the study site, these visit procedures may be scheduled over a longer time period of up to 2 weeks.

*Procedures:* **See each drug-specific appendix for the specific assessments that are required at each visit.** Procedures may include any of the following:

- Medical/treatment history, including:
  - Concomitant medications
  - Assessment /recording of adverse events
- Urine pregnancy testing, if applicable
- Laboratory sample collection (e.g., drug-specific tests, stored plasma and/or serum, and clinical safety assessment as outlined in the drug-specific appendices)
- Administration of C-SSRS
- Vital signs (blood pressure, heart rate, respiratory rate, body temperature, weight and height)
- Physical and neurological examinations

- Clinical assessments:
    - CDR, including calculation of CDR-SB
    - NPI-Q
    - GDS
    - FAS
    - MMSE
    - Assessment of clinical diagnosis and clinician judgment of symptoms
- NOTE:** For each subject, the CDR and assessment of clinical diagnosis should be administered by the same experienced clinician at all visits. Whenever possible, the CDR rater should not be involved in other clinical assessments (e.g., MMSE, FAS, GDS, NPI-Q) or in cognitive testing.
- 12-lead ECG
  - Cognitive testing
  - MRI (should be performed before lumbar puncture, if on the same date)
  - Lumbar Puncture (LP) for CSF collection (water is allowed and encouraged). Site staff should contact the subject 24-48 hours after the LP to assess for adverse effects of the LP.
  - PET imaging
  - Study drug administration
  - Site phone call (not required after all off-site visits but direct site-subject contact should occur at least once every 3 months throughout the study): the DIAN-TU site coordinator calls subject and addresses any concerns, discusses scheduling of safety MRI and/or next visits, and encourages compliance.

### 6.3.5 End-of-Treatment / Safety Follow-up Visit

The double-blind treatment period for each subject may vary based on when the subject was enrolled and may last from 4 (208 weeks [V54]) up to 7 years (364 weeks [V93]) or until early termination, whichever is sooner. Subjects will continue treatment with the assigned study drug until every subject randomized to the study drug arm has received a minimum of 4 years (208 weeks) of treatment or is withdrawn, at which time study treatment will be discontinued for all subjects in the study drug arm and all subjects should be scheduled for an end-of-treatment/safety follow-up visit. Based on the date of the last subject randomization (December 2015), the last subject will have received 4 years treatment and all double-blind treatment visits will be concluded by November 2019. Any visits scheduled to occur on or before the sponsor-specified cut-off date (November 2019) should be conducted as usual and will be the final dosing visits for all subjects. All subjects will then be scheduled for their respective end-of-study or safety follow-up visit relative to the subject's last dose within their drug-specific visit window.

*Location:* Procedures/contacts may be accomplished at the DIAN-TU site or subject's home or other trial-identified location with the trial-designated home health nurse.

*Timing:* The end of treatment/safety follow-up visit should be performed between 4 and 12 weeks (+/- 7 days) after the subject's last dose of double-blind treatment. The sequence and timing of visit procedures is very important and are detailed in the *Global Manual of Operations*.

Procedures **may** include any of the following:

- Concomitant Medications
- Adverse Event Assessment
- Vital signs (blood pressure, heart rate, respiratory rate, body temperature, weight)
- 12-lead ECG
- Administration of C-SSRS
- Laboratory sample collection (e.g., drug-specific tests, and clinical safety assessment as outlined in the drug-specific appendices)
- Urine collection for urinalysis

Any procedures done after the last dose, but before the safety follow-up visit, may not need to be repeated. **See each drug-specific appendix for the specific assessments that are required at each visit.**

6.3.6 [REDACTED]

[REDACTED]

[REDACTED]

[REDACTED]

[REDACTED]

[REDACTED]

[REDACTED]

[REDACTED]

[REDACTED]

[REDACTED]

[REDACTED]

[REDACTED]

- [REDACTED]
- [REDACTED]
- [REDACTED]
- [REDACTED]
- [REDACTED]

measures (e.g., drug-specific tests, stored plasma and/or serum) per drug-specific

- [REDACTED]
- [REDACTED]
- [REDACTED]
- [REDACTED]
- [REDACTED]
- [REDACTED]
- [REDACTED]
- [REDACTED]
- [REDACTED]
- [REDACTED]

- [REDACTED]

### 6.3.7 Early Termination/Post-treatment Follow-up

If a subject withdraws, is terminated from the study prior to completion of the double-blind treatment period, or is in a study drug arm that is stopped prior to the end of the double-blind treatment period, every effort should be made to schedule an early termination visit. PET imaging studies may be omitted if early termination occurs less than 6 months after the previous PET imaging or if precluded by local regulations/dosimetry limits. Other procedures may also be eliminated on a case-by-case basis, as determined by the sponsor or if not required based on the study drug arm procedures or study period.

Any subject that meets study drug discontinuation criteria per section 4.4.1 (excluding subjects who are known mutation negative) will be encouraged to continue participation in any of the scheduled clinical, cognitive, and/or biomarker assessments that are able to be performed even though dosing has concluded. The determination of which assessments to be attempted/completed will be decided with the site principal investigator and sponsor based on the subject's capabilities, the benefit to the study, and the risk associated with continued participation at the time of study drug discontinuation. The level of continued participation may change if/as the subject's status changes.

*Location:* DIAN-TU site or at the subject's home or other trial-identified location with the trial-designated home health nurse

*Time/Timing:* The early termination visit may occur at any time during the study. Approximately a 3-4 day visit. For subjects who live near the study site, these visit procedures may be scheduled over a longer time period of up to 2 weeks.

*Procedures:* **See each drug-specific appendix for the specific assessments that are required at each visit.** Procedures may include any of the following:

- Medical/treatment history, including:
  - Concomitant medications

- Assessment /recording of adverse events
  - Laboratory sample collection (baseline drug-specific tests, stored plasma and/or serum, and clinical safety assessment)
  - Administration of C-SSRS
  - Vital signs (blood pressure, heart rate, respiratory rate, body temperature, weight and height)
  - Physical and neurological examinations
  - Clinical assessments:
    - CDR including calculation of CDR-SB
    - NPI-Q
    - GDS
    - FAS
    - MMSE
    - Assessment of clinical diagnosis and clinician judgment of symptoms.
- NOTE:** For each subject, the CDR and assessment of clinical diagnosis should be administered by the same experienced clinician at all visits. Whenever possible, the CDR rater should not be involved in other clinical assessments (e.g., MMSE, FAS, GDS, NPI-Q) or in cognitive testing.
- 12-lead ECG
  - Cognitive testing
  - MRI (structural and functional) (should be performed before lumbar puncture, if on the same date)
  - Lumbar Puncture (LP) for CSF collection (water is allowed and encouraged). Site staff should contact the subject 24-48 hours after the LP to assess for adverse effects of the LP.
  - PET imaging
  - Drug reconciliation as specified in each drug-specific appendix

#### 6.4 Termination of the Study

The sponsor may terminate the study or study-drug arm, [REDACTED] at any time. Furthermore, if it becomes apparent that subject enrollment is unsatisfactory with respect to quantity or quality, or that data recording is inaccurate or incomplete on a chronic basis, the sponsor has the right to terminate the study and remove all study materials from the investigational site. A written statement will be provided to the investigator, IRB/IEC, and regulatory authorities, if required. If any SAEs are reported as part of the reason for early termination of the study, all documentation relating to the event(s) reported to regulatory authorities must be obtained and filed appropriately. The DSMB may recommend termination of the study or study drug arm but final decisions will be made by the sponsor. [REDACTED]

## 7 SAFETY AND ADVERSE EVENTS

### 7.1 Definitions

#### 7.1.1 Adverse Events

An adverse event (AE) is defined as any untoward medical occurrence in a subject administered study drug, whether or not considered drug related. An adverse event can be any unfavorable and unintended sign (including abnormal laboratory findings), symptom, or disease temporally associated with the use of the study drug, whether or not considered related to study drug. An adverse event can arise from any use of the drug and from any route of administration, formulation, or dose including an overdose.

Any medical condition that is present at the time the subject is consented but does not deteriorate should not be reported as an AE. However, if it deteriorates or worsens significantly at any time during the study, it should be recorded as an AE.

Clinically meaningful (for a given subject) changes in physical examination findings and abnormal objective test findings (e.g., laboratory, vital signs, ECG, imaging (e.g., definite new ARIA changes) should also be recorded as AEs. The criteria for determining whether an abnormal objective test finding should be reported as an AE are as follows:

1. Test result is associated with accompanying symptoms or is of clinical concern
2. Test result requires additional diagnostic testing or medical/surgical intervention
3. Test result leads to a change in study dosing or discontinuation from the study, significant additional concomitant drug treatment, or other therapy
4. Test result leads to any of the outcomes included in the definition of a SAE

Merely repeating an abnormal test, in the absence of any of the above conditions, does not meet criteria 2 above for reporting as an AE. Any abnormal test result that is determined to be an error does not require reporting as an AE.

**NOTE:** *The following are not considered AEs or SAEs:*

- **Preplanned surgeries or procedures:** Preplanned procedures (surgeries or therapies) that were scheduled prior to signing of informed consent are not considered AEs. However, if a preplanned procedure is performed early (e.g., as an emergency) due to a worsening of the pre-existing condition, the worsening of the condition should be captured appropriately as an AE. Complications resulting from any planned surgery should be reported as AEs.
- **Elective surgeries or procedures:** Elective procedures performed where there is no change in the subject's medical condition should not be recorded as AEs, but should be documented in the subject's source documents. Complications resulting from an elective surgery should be reported as AEs or SAEs (depending on the severity).

- **Insufficient clinical response (lack of efficacy):** Insufficient clinical response, efficacy, or pharmacologic action, should NOT be recorded as an AE. The principal investigator must make the distinction between exacerbation of pre-existing illness and lack of therapeutic efficacy.

### 7.1.2 Serious Adverse Event

If any adverse event meets any of the following criteria in the view of either the investigator or sponsor, it is to be reported to the safety group as a serious adverse event (SAE) within 24 hours of occurrence or notification of the site:

- **Death of subject.** An event that results in the death of a subject.
- **Life-Threatening.** An event that, in the opinion of the investigator, would have resulted in immediate fatality if medical intervention had not been taken. This does not include an event that would have been fatal if it had occurred in a more severe form.
- **Inpatient Hospitalization.** An event that results in the admission to the hospital for any length of time. This does not include an emergency room visit or admission to an outpatient facility.
- **Prolongation of existing hospitalization.** An event that occurs while the study subject is hospitalized and prolongs the subject's hospital stay.
- **A persistent or significant disability/incapacity.** An event that results in a condition that substantially interferes with the activities of daily living of a study subject. Disability is not intended to include experiences of relatively minor medical significance such as headache, nausea, vomiting, diarrhea, influenza, and accidental trauma (*e.g.*, sprained ankle).
- **Important medical event requiring medical or surgical intervention to prevent serious outcome.** An important medical event that may not be immediately life-threatening or result in death or hospitalization, but based on medical judgment may jeopardize the subject and may require medical or surgical intervention to prevent any of the outcomes listed above (*i.e.*, death of subject, life-threatening, hospitalization, prolongation of hospitalization, congenital anomaly, or persistent or significant disability/incapacity). Examples of such events include allergic bronchospasm requiring intensive treatment in an emergency room or at home, blood dyscrasias or convulsions that do not result in inpatient hospitalization, or the development of drug dependency or drug abuse.
- **Congenital anomaly/birth defect.** An anomaly detected at or after birth, or any anomaly that results in fetal loss.
- **Suspected Hy's law case (should be reported as serious unexpected adverse event).**

### 7.2 Adverse Event (AE) Severity

The intensity of the AE will be rated by the investigator as mild, moderate or severe using the following criteria:

**Mild:** an event that is transient and easily tolerated by the subject; requires minimal or no treatment and does not interfere with the subject's daily activities.

**Moderate:** an event that causes the subject discomfort and may cause some interference in the subject's usual activities.

**Severe:** an event that causes considerable interference with the subject's usual activities, may require drug therapy or other treatment, and may be incapacitating or life-threatening.

### 7.3 Relationship to Study Drug

The relationship of an AE to study drug, imaging agents (e.g., [C]PiB and F tracers) and or study procedures should be assessed by the principal investigator using the following guidance:

**Definite.** An event, including laboratory test abnormality, which:

- a. Occurs within a reasonable temporal sequence to administration of study drug,
- b. Cannot be explained by concurrent disease or other drugs or chemicals
- c. Improves or disappears on stopping or reducing study drug (dechallenge)
- d. Reappears on repeated exposure to study drug (rechallenge)
- e. Is an unusual event that is known to be associated with the drug or this class of compound, and cannot be explained by other therapy or the subject's physical condition.

**Probable/Likely.** An event, including laboratory test abnormality, which:

- a. Occurs within a reasonable temporal sequence to administration of study drug,
- b. Unlikely to be attributed to concurrent disease or other drugs or a clinically reasonable response on withdrawal (dechallenge)
- c. Rechallenge was not attempted.

**Possible.** An event, including laboratory test abnormality, which:

- a. Occurs within a reasonable temporal sequence to administration of study drug, but
- b. Could also be explained by concurrent disease or other drugs or chemical
- c. Information on drug withdrawal may be lacking or unclear.

**Unlikely.** An event, including laboratory test abnormality, which:

- a. Occurs with a temporal relationship to administration of study drug which makes a causal relationship improbable, and
- b. In which other drugs, chemicals or underlying disease provide plausible explanations.

**Definitely Not.** An event, including laboratory test abnormality, which is known to be associated with the subject's clinical condition, or with other medication taken by the subject.

#### **7.4 Adverse Event Collection Period**

All AEs reported from the time that informed consent is obtained until 30 days following the last dose of study drug [REDACTED] will be collected, whether elicited or spontaneously reported by the subject. Adverse events should be collected at End of Study and Early Termination visits even if these visits occur more than 30 days after last dose of study drug. Serious adverse events considered related to study drug or procedures should be reported even if they occur more than 30 days after the last dose of study drug.

At every study visit, subjects will be asked a standard question to elicit any medically related changes in their well-being. They will also be asked if they have been hospitalized, had any accidents, used any new medications, or changed concomitant medication regimens (both prescription and over-the-counter medications).

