## 7.7 Pregnancy Reporting

Cases of pregnancy that occur during maternal or paternal exposures to study drug or within 16 weeks following last dose of study drug should be reported. Data on fetal outcome and breast-feeding are collected for regulatory reporting and drug safety evaluation. Sites should report pregnancies to █████ Safety in the same manner and timing as for Serious Adverse Events specified in section 7.6.

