### 3.3.15 End of Study Visit

*Location:* DIAN-TU site or subject's home or other trial-identified location with the trial-designated home health nurse.

*Timing:* The end of study safety follow-up visit should be performed 12 weeks (+/- 7 days) after the last dose of double-blind treatment.

*Procedures:*

- Concomitant Medications
- Adverse Event Assessment
- Vital signs (blood pressure, heart rate, respiratory rate, and body temperature; weight may be obtained approximately every 3 months per section 6.1.6 of main protocol)
- Clinical laboratory tests
- Serum pregnancy testing for women of childbearing potential

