### 3.3.16 End-of-Treatment Safety Follow-up Visit

The double-blind treatment period for each subject may vary based on when the subject was enrolled and may last from 4 up to 7 years (364 weeks [V93]) or until early termination, whichever is sooner. Subjects will continue treatment with the assigned study drug until every subject randomized to this study drug arm has received a minimum of 4 years (208 weeks) of treatment or is withdrawn, at which time study treatment will be discontinued for all subjects

in the solanezumab study arm and all subjects should be scheduled for an end-of-treatment safety follow-up visit.

*Location:* Procedures/contacts may be accomplished at the DIAN-TU site or subject's home or other trial-identified location with the trial-designated home health nurse.

*Timing:* The end-of-treatment safety follow-up visit should be performed 4 to 8 weeks (+/- 7 days) after the subject's last dose of double-blind treatment.

*Procedures\*:*

- Concomitant Medications
- Adverse Event Assessment
- Vital signs (blood pressure, heart rate, respiratory rate, body temperature, weight)
- 12-lead ECG
- Blood draw for:
  - Clinical laboratory tests (hematology, chemistry, urinalysis)
  - Serum pregnancy testing for women of childbearing potential
  - Drug-specific testing (section 1.12) serum for anti-solanezumab antibodies; plasma for amyloid beta peptide and solanezumab levels
- Urine collection for urinalysis

\*Any procedures done after the last dose, but before the safety follow-up visit, do not need to be repeated.

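### Solanezumab's last scheduled safety contact can fall before the protocol's 30-day adverse event period ends, neither arm's reaches the 16-week pregnancy window, and its application to early leavers is unclear

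*Protocol*

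**What the plan says.** **Collection and reporting periods.** Main protocol section 7.4 collects "All AEs reported from the time that informed consent is obtained until 30 days following the last dose of study drug", "whether elicited or spontaneously reported by the subject". It adds that "Adverse events should be collected at End of Study and Early Termination visits even if these visits occur more than 30 days" after the last dose, and that "Serious adverse events considered related to study drug or procedures should be reported even if they occur more than 30 days" after it. Section 7.7 says that pregnancies during maternal or paternal exposure or "within 16 weeks following last dose of study drug should be reported". Inclusion criterion 3 in section 4.1 requires contraception over the same 16 weeks.

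**Last scheduled visit.** In the solanezumab arm (Appendix 4, section 3.3.16) the visit "should be performed 4 to 8 weeks (+/- 7 days) after" the last dose. In the gantenerumab arm (Appendix 3, section 3.3.15), "The end of study safety follow-up visit should be performed 12 weeks (+/- 7 days) after the last dose of double-blind treatment". Main protocol section 6.3.5 spans both arms with a range of 4 to 12 weeks, also plus or minus 7 days. In both appendices this visit is the last column of the double-blind schedule.

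**Early leavers.** Section 6.3.7 asks for every effort to hold an early termination visit and states: "The early termination visit may occur at any time during the study". Appendix 3 section 3.3.16 and Appendix 4 section 3.3.17 give that visit all Visit 54 procedures (Visit 93 for later leavers). The schedules list adverse event assessment and pregnancy testing there.

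**The concern.** A protocol that commits to collecting adverse events to day 30, elicited or spontaneous, would be expected to ask about them at or after day 30 at least once. In the solanezumab arm a fully compliant last visit can come earlier. Anything that starts between that visit and day 30 is then recorded only if the subject volunteers it. In both arms the same holds for pregnancies in the later part of the 16-week window, since no scheduled contact reaches its end.

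For subjects who stop early, the one visit clearly assigned to them has no stated interval from the last dose. A site cannot tell from the text whether the timed safety visit is also due. What is at stake is the completeness of prompted safety ascertainment just after treatment ends.

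**Working it through.** The plan states no figure for this gap, so there is none to reproduce. The check is calendar arithmetic on its own windows.

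**Inputs**
- Adverse event period: 30 days after the last dose (section 7.4).
- Pregnancy window: 16 weeks = 16 × 7 = 112 days (section 7.7).
- Solanezumab visit: 4 to 8 weeks ± 7 days (Appendix 4, section 3.3.16).
- Gantenerumab visit: 12 weeks ± 7 days (Appendix 3, section 3.3.15).
- Main protocol visit: 4 to 12 weeks ± 7 days (section 6.3.5).

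**Formulas**
- Earliest day = 7 × lower bound in weeks − 7. Latest day = 7 × upper bound in weeks + 7.
- Adverse event shortfall = max(0, 30 − visit day).
- Pregnancy shortfall = 112 − visit day.

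**Visit days**
- Solanezumab: 28 − 7 = 21 to 56 + 7 = 63; nominal 28 to 56.
- Gantenerumab: 84 − 7 = 77 to 84 + 7 = 91; nominal 84.
- Main protocol: 28 − 7 = 21 to 84 + 7 = 91; nominal 28 to 84.

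**Shortfalls in days**

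| Source | Visit day | Adverse events (30) | Pregnancy (112) |
|---|---|---|---|
| Solanezumab | 21 | 9 | 91 |
| | 28 | 2 | 84 |
| | 56 | 0 | 56 |
| | 63 | 0 | 49 |
| Gantenerumab | 77 | 0 | 35 |
| | 84 | 0 | 28 |
| | 91 | 0 | 21 |
| Main protocol | 21 | 9 | 91 |
| | 28 | 2 | 84 |
| | 84 | 0 | 28 |
| | 91 | 0 | 21 |

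The adverse event shortfall therefore arises only under the solanezumab timing, and under the main protocol's lower bound. It disappears for any visit at or after day 30. The pregnancy shortfall is present at every permitted visit day in both arms.

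**Early leavers: the passages side by side**
- *Arm-end wording.* Main protocol section 6.3.5 and Appendix 4 section 3.3.16 say that treatment stops for everyone once every subject in the arm has 4 years or has withdrawn, and that all subjects are then scheduled for the follow-up visit. Read this way, a subject who left years earlier is not obviously included. Appendix 4 section 3.3.17 also places the end-of-study drug-specific tests in the termination visit, which hints that it stands in for the follow-up.
- *Subject-level wording.* The same sections time the visit from the subject's own last dose. Footnote 10 to the beyond-year-4 schedule in each appendix requires the visit after the last dose, and describes the double-blind period as lasting until early termination if that is sooner. Read this way, early leavers are included.

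Both readings are open.

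**The case against.** The strongest reply is that a reporting period is not a visit window. Section 7.4 accepts spontaneous reports, and related serious events have no end date. Sections 7.5 and 7.6 require known events to be followed to resolution or stability. Pregnancy reporting includes paternal exposure, which testing the subject could never detect. The 9 days is also the extreme corner of the window. And the section 7.4 sentence is redacted just after the words quoted, so a qualifier may be hidden.

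Most of this stands, and it confines the point to prompted ascertainment: no reporting duty lapses. It does not remove the point. Following known events to resolution does not find new ones that start after the last visit, and a nominal 4-week visit is still early. The next two sentences of section 7.4 use the same 30-day mark, so the redaction is unlikely to change the arithmetic.

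Three stronger readings are tempting, and the documents do not support them:
- *Early leavers have no contact after dosing.* They have the termination visit with adverse event assessment and pregnancy testing, and section 6.3.7 encourages continued assessments. The exception is subjects withdrawn after learning that they are mutation negative (section 4.4.1), who were assigned to placebo.
- *Unequal follow-up biases pooled placebo comparisons.* The safety endpoints are treatment-emergent events, and their cut-off is normally set in the SAP, which is not at hand.
- *About a fifth of active subjects are affected.* The planned 52 − 42 = 10 leavers of 52 (19%) is assumed all-cause attrition over 4 years. The protocol gives no share that stops for safety.

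**Conclusion.** The mismatch is real but modest.

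- **Solanezumab, adverse events:** the last scheduled contact can precede the end of the 30-day period by up to 9 days, or 2 days at a nominal 4 weeks. Gantenerumab is not affected.
- **Both arms, pregnancy:** the last scheduled contact always precedes the end of the 16-week window, by 49 to 91 days (7 to 13 weeks) for solanezumab and 21 to 35 days (3 to 5 weeks) for gantenerumab.
- **Early leavers:** the termination visit has no minimum interval from the last dose, and the protocol is ambiguous on whether the timed visit also applies.

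This rests on taking the visit windows at face value, on the follow-up visit being the last contact of the double-blind period, and on no relevant qualifier lying under the redaction in section 7.4. It shows a gap in scheduled, prompted enquiry. It does not show how many events would be missed, and the documents give no basis for estimating that.

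**What to change.** 1. Reconcile main protocol section 6.3.5 and Appendix 4 section 3.3.16 with section 7.4, so that the last scheduled adverse event contact, by visit or coordinator call, does not precede the end of the protocol's own 30-day period.
2. State in section 6.3.7 and in the early termination sections of both appendices that this contact applies to subjects who stop early, and bring the arm-end wording into line with footnote 10 of the schedules.
3. Reconcile the pregnancy window in section 7.7 with the last scheduled contact in each arm, or say plainly that the remainder of the window relies on unprompted reports.

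The cost is wording and at most a call or two. The schedules already have coordinators in contact with subjects at least every 3 months during treatment. The downside is slightly later closure of each subject.
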